# 1. Study Synopsis

TITLE OF STUDY:	Lithium orotate: a potential accessible supplement for people experiencing depression with mixed features.
Protocol Short Title/ Acronym:	MixLi
Study Phase If Not Mentioned In Title:	Feasibility open label study
Sponsor Name:	King's College London & South London and Maudsley NHS Foundation Trust
Chief Investigator:	[name]

Medical Condition or Disease Under Investigation:	Episode of major depression with mixed features	
Purpose Of Clinical Study:	To establish initial feasibility of studying a commercially available supplement (lithium orotate; LiOr) for its potential mood effects in people with depression including mixed features (DMF).	
	This is a feasibility study comprising the preliminary work required, prior to formal (initially feasibility) trials examining commercially available LiOr supplementation for people with DMF. A single arm open label study in volunteers with DMF will explore four co-primary objectives: 1. The potential to examine bioavailability of LiOr, assessing lithium levels in	
Primary Objective:	
 
2. The acceptability of 20mg daily LiOr over 6 months (assessed by self-report adherence and discontinuation rates) to inform a future study design.
 
	
	3. Description of positive and/or negative effects of 20mg daily LiOr over 6 months (assessed via participant-report) to inform a future study design.	
	4. The feasibility of the protocol including intervention delivery and assessment visits (including assessments mentioned above, plus putative primary (depressive and (hypo)manic symptoms) and key secondary outcomes (functioning, cognition) as well as assessment of potential confounders. Overall feasibility will be assessed via missing data and study withdrawal rates.	
	Exploratory analysis of change in measures over time to inform a future definitive study design:	
Secondary Objective(s):	1. Biological measures: (1) key candidate blood-based biomarkers, namely neuroprotective growth factors (BDNF, VEGF) and inflammatory cytokines (IL-6, TNFα, IL-1b, IL-8, CRP).	
	
 
Symptom measures (mood symptoms, both depressive and (hypo)manic).
 
Functional measures (psychosocial functioning and cognition).
 
	
Study Design:	The study is a single site, unblinded single arm open label study of LiOr for people with DMF.	
	Throughout the protocol, week 0 refers to the baseline assessments; all other references to "week" timepoints anchor from week 0.	
Endpoints:	Week 0: Baseline assessment, pre-intervention	
	Week 2, 4, 8, 16: Intermediary follow-up assessments Week 26: Final follow-up assessment	
Sample Size:	40 individuals.	

Summary Of Eligibility Criteria:	Aged between 18-65 at study entry. Meet DSM-5 criteria for a current depressive episode and exceed thresholds indicating presence of mixed features. Undergoing antidepressant treatment (stable intervention/dose unchanged for >6 weeks). No diagnosis of bipolar disorder received. No other severely impairing health condition. No contraindications to lithium treatment (including currently taking lithium). No significant suicidality.		
Intervention (Description, frequency, details of delivery):	Open label lithium orotate supplement as available commercially, 20mg once per day. Participants will be instructed to begin taking the supplement the day after the baseline assessment for a period of up to six months. If participants prefer to move to a lower dose, they can titrate down to 15mg, 10mg or 5mg. Intervention is self-managed, but participants are provided with information about the supplement and have access to the research team to answer any questions or provide further information. Participants who discontinue will remain in the study, although will not be required to attend intermediary follow- up visits, which collect information related to the intervention. We will ask them to attend the final endpoint visit, however.		
Comparator Intervention:	n/a		
Maximum Duration Of Treatment Of A Participant:	6 months / 26 weeks (i.e., from baseline up until the final follow-up assessment). Participants are permitted to discontinue the supplement at any time they wish.		
Version And Date Of Final Protocol:	[to be completed]		
Version And Date Of Protocol Amendments:	n/a as yet		

# 2. Revision History

Document ID – (Document Title) revision X.Y	Description of changes from previous revision	Effective Date

## 3. Glossary of terms

**ACEI:** Angiotensin-Converting Enzyme Inhibitors AE: adverse event [name]: [name] **ANOVA:** Analysis of variance **AR:** adverse reaction **ARB:** Angiotensin receptor blockers ASRM: Altman Self-Rating Mania Scale **BD:** bipolar disorder BDNF: brain-derived neurotrophic growth factor CI: chief investigator CRF: clinical research facility **CRP:** c-reactive protein DMF: depression with mixed features EQ5D: Eurogol health-related quality of life measure FAST: Functional assessment short test GAD7: Generalised anxiety disorder 7-item questionnaire GCP: good clinical practice HCL: hypomanic checklist HTA: human tissue act **IME:** important medical event ID: identification code **IDS:** Inventory of depressive symptoms **IQR:** Inter-quartile range **IRAS:** integrated research application system ISRCTN: international Standard Randomised Controlled Trial Number **ISS:** internal states scale KCL: King's College London LiOr: lithium orotate supplement LiSERS: Lithium Side Effects Rating Scale M3VAS: Maudsley 3-item visual analogue scale MixLi: the lithium supplement study for depression with mixed features MDD: Major depressive disorder NHS: national health service (UK) NIHR: national institute for health research NSAID: non-steroidal anti-inflammatory drugs PI: principal investigator PIS: participant information sheet **PPI:** patient and public involvement **REC:** research ethics committee RCT: randomised controlled trial RS: [name] SAE: serious adverse event SAP: statistical analysis plan

SAR: serious adverse reaction SD: standard deviation SLaM: South London & Maudsley NHS Trust SOP: standard operating procedure SSC: study steering committee SUSAR: suspected unexpected serious adverse reaction TEMPS: Temperament Evaluation in Memphis, Pisa and San diego THINC-IT: THINC-it cognitive screening tool TRQ: tablets routine questionnaire UAR: unexpected adverse reaction UK: United Kingdom VEGF: vascular endothelial growth factor YMRS: Young mania rating scale

# 5. Background & Rationale

Lack of access to best-practice treatment is extremely common both in unipolar1 and bipolar2,3 affective disorders. Undertreatment is especially an issue for people experiencing depression with mixed features (DMF),4

where criteria for a depressive episode are met alongside concurrent symptoms of mania (e.g., activation, increased thought and speech rate).4 DMF is common5 and highly burdensome, not only with regard to a scant evidence base for effective treatments4 but also associations with bipolar disorder (progression to diagnosis or risk thereof)6, suicidality7 and psychosocial (including cognitive) disability.8 Moreover, DMF is under-detected in healthcare services and patients are routinely treated with standard antidepressant medications.4 These medications confer risk in DMF for worsening the manic symptom severity.4 Concomitant treatment with an antidepressant and a mood stabiliser could improve outcomes4,6, but this treatment strategy is rarely used in those without a full bipolar diagnosis.1,9

The gold standard mood stabiliser is lithium, usually prescribed in carbonate or citrate form.3 Despite its effectiveness against both symptoms of depression and (hypo)mania, including bipolar DMF,10 lithium is underused not least because the prescribed forms require regular blood monitoring to ensure patient safety.3 Thus, despite its putative effectiveness for people with DMF without a bipolar diagnosis, lithium is not routinely available for this population.

Our recent systematic review indicates effectiveness of lithium at 'sub-therapeutic' doses to patients with depression, mania and cognitive impairment (from 17 studies assessing intervention with lithium as low as 0.3mg elemental lithium.11 This is in contrast to 'therapeutic' doses, which average ~600-800mg lithium carbonate (containing >112mg ionic lithium).

This is pertinent because these low doses are also evidenced to be safe, and a low-dose form of lithium (lithium orotate; LiOR) is available to purchase cheaply (without a prescription) as a supplement (up to 20mg ionic lithium) with our early work indicating that even lower doses (5 mg) result in detectable brain levels of lithium.12 If evidenced to be effective, LiOR could therefore be an accessible treatment option. My PPI work suggests it may also be desirable for patients, being a 'natural' substance. Despite evidence of safety11,12 LiOr has not been subject to clinical trials.11 This project seeks to determine whether commercially available LiOr has viability as an accessible adjunctive intervention for people with DMF.

# 6. Study Objectives and Design

## 6.1. Study Objectives

This research aims to elucidate LiOr's plausibility, at a known safe dose, over an extended period in a preliminary study. This is a feasibility study comprising the preliminary work required prior to formal trials examining commercially available LiOr supplementation for DMF. No specific hypotheses are therefore proposed. In this open label study, people who constitute a target population for LiOR will be invited to take commercially available LiOr for up to six months to establish its plausibility as a putative intervention for trials. The specific objectives are to investigate up to six months of open-label 20mg daily LiOr to identify its within-subjects effects on the following as co-primary outcomes:

1. The potential to examine bioavailability of LiOr (i.e. whether lithium is present at detectable levels in the serum using a standard laboratory lithium test), assessing lithium levels in serum.

2. The acceptability of 20mg daily LiOr over 6 months (assessed by self-report adherence and discontinuation rates) to inform a future study design.

3. Description of any positive and/or negative experiences of 20mg daily LiOr over 6 months (assessed via participant-report) to inform a future study design.

4. The feasibility of the protocol including intervention delivery and assessment visits (including assessments mentioned above, plus putative primary (mood) and secondary (functioning, cognition) outcome measures and assessment of potential confounders). Overall feasibility will be assessed via missing data and study withdrawal rates.

An exploratory analysis of change will be undertaken as secondary objectives for measures over time to inform a future definitive study design:

1. LiOR's biological effects, through assessment of key candidate blood-based biomarkers, namely neuroprotective growth factors (BDNF, VEGF) and inflammatory cytokines (IL-6, TNFa, IL-1b, IL-8, CRP) between week 0 and week 26.

2. LiOr's effects on mood, through assessing changes in mood ratings between week 0 and week 26.

3. LiOr's effects on cognition and functioning, through assessing changes in cognitive and psychosocial function between week 0 and week 26.

These aims will be met via within-subjects comparisons for each timepoint relative to baseline (weeks 2, 4, 8, 16, 26).

#### 6.2. Study Design

A single site, one arm unblinded open label study investigating the effects of LiOr supplementation (20mg, once per day) for up to six months. We will recruit 40 people for this feasibility study.

#### 6.3. Study Flowchart

Table 1: Summary of study procedures and measures.

Procedures/Measures	Screening	Baseline (W0)	Intermediary (W2, 4, 8, 16)	Follow-up (W26)
Eligibility assessment [questions, MINI suicide, bipolar, & MDD  ,	Х			
Informed consent		Х		
LiOr provision		Х	Х	
Patient information	Х			
Sociodemographic		Х		х
Illness history [questions, HCL  , TEMPS 16* ]		Х		
Service use and health-related quality of life (EQ5D) 		Х		Х
Cognitive battery (THINC-IT  )		Х	Х	Х

Procedures/Measures	Screening	Baseline (W0)	Intermediary (W2, 4, 8, 16)	Follow-up (W26)
Mood self- (ASRM  / M3VAS  / GAD7  / ISS  ) & investigator- report (IDS  / YMRS 		Х	Х	х
Functioning [FAST  ]		Х		Х
Blood test	Х	Х	Х	Х
Subjective experiences (LiSERS  )			Х	Х
Adherence (TRQ  )			Х	Х

## 7. Study Intervention

#### 7.1. Therapy/Intervention Details

This section relates to the lithium orotate (LiOR) supplementation (N=40). The study will not interfere with usual care in any way, although the study team will inform participants' named healthcare professionals (GPs or secondary care clinician if under outpatient care) of their participation which includes LiOR supplementation. LiOr is available in 5mg, 10mg or 20mg doses. As our previous research has shown that individuals frequently take 20mg LiOR once per day of their own accord, without need for titration, we encourage participants to start from this dose. We do not permit a higher dose, as there is no evidence to date of commercial LiOR supplementation at these doses. We will permit a lower dose, if participants desire: as capsules are 5mg each, participants can select to take fewer capsules daily and we will collect this information. We will measure the rates and duration of doses taken. We will support participants if they have questions. Participants will receive bottles/pots as can be purchased, which contain 60 x 5mg capsules (which covers up to 20mg per day for 15 days). Between weeks 0 -2, and 2 – 4, one supply can be provided at the earlier time until the upcoming visit. Subsequently, or if visits are not conducted within 15 days (i.e., participants would otherwise have depleted supply), the next supply of LiOR will be delivered via special delivery Royal Mail with receipt confirmed. This will be undertaken on the basis of checking with participants regularly the quantity of LiOR they have remaining to ensure a continual supply. At the 26-week assessment, participants will be asked to return any remaining LiOR. The lithium orotate purchased is manufactured by Swanson www.swanson.co.uk. [name] team at Newcastle University have examined the quantity and consistency (both within and between batches) determining these to be accurate and stable. Swanson have provided King's Clinical Trial Unit with quality documents (including demonstration of quality, purity and potency at the point of release of the product onto the market, and over-time). These were reviewed by the CTU's pharmacist who has confirmed appropriateness for progressing in the study with these. The supplement will be purchased directly from the supplier and stored in locked cupboards, in a locked office at King's College London, that only the research team will have access to. These will be a cool, dry place as per manufacturer instructions and we will ensure that the product expiry date outlives the date to participants' next supply date. Records will be kept of distribution to participants as per above. The products will not be unsealed or altered in any way before distribution to participants.

#### 7.2. Intervention timeline

The intervention will begin at the start of Week 1, the day after baseline assessment. The intervention will continue for 6 months, until the final assessment at week 26, or as long as participants are willing to continue with the intervention during this time.

#### 7.3. Intervention adherence

Adherence will be examined via completion of the participant-reported, validated Tablets Routine Questionnaire. A TRQ score equating to 80% adherence is a conservative threshold for dichotomous adherence definition. (see Section 10 for more details).

#### 7.4. Concomitant treatments (usual care)

All participants will continue receiving TAU including all concomitant interventions and service use. We will monitor and record these. In addition to monitoring at each assessment, participants are asked to inform the team immediately of any new intervention they have been prescribed and/or are considering initiating, to ensure these have no potential contraindications with the study supplement.

## 8. Research environment

The study will take place in one location. The Clinical Research Facility (CRF) at King's College Hospital will be used for all study procedures (blood tests, interviews and questionnaires), but the screening assessment will be conducted via telephone/videocall. The CRF is a purpose-built facility to support clinical trials and provides ideal infrastructure for studies of this nature (biological testing and processing facilities, quiet, private rooms with appropriate space for testing materials).

## 9. Selection and Withdrawal of Participants

#### 9.1. Inclusion Criteria

Participants will be:

1) Aged between 18-65 at study entry.

2) Meet DSM-5 criteria for a current depressive episode (MINI) and exceed thresholds indicating presence of mixed features (Internal States Scale; ISS).

3) Undergoing stable pharmacological treatment for depression (intervention/dose unchanged for >6 weeks).

- 4) Willing to try a commercially available lithium supplement.
- 5) Willing to attend planned study visits.

#### 9.2. Exclusion Criteria

People meeting any of the following criteria will be excluded:

1) Clinical diagnosis of bipolar disorder.

2) Other health condition that is severely impairing (as per self-report).

3) Known contraindication to lithium treatment. This includes currently taking lithium. These are derived from those applicable to medically prescribed forms of lithium. Although these are not established contraindications to microdoses of lithium, we are including them to fully ensure no ill effects to our study participants. These include:

- Known allergy to lithium or its excipients
- Known cardiac disease or cardiac insufficiency
- Known renal impairment
- Known untreated thyroid dysfunction
- Breast-feeding or pregnant
- Known hyponatraemia or frequent dehydration
- Addison's disease

- Brugada syndrome or family history of Brugada syndrome
- Psoriasis
- Upcoming use of, unable or unwilling to abstain from using any of the following medications during the upcoming 6 months:

- non-steroidal anti-inflammatory drugs (NSAID) or cyclo-oxygenase-2inhibitors i.e., aceclofenac, acemetacin, celecoxib, dexibuprofen, dexketoprofen, diclofenac, diflunisal, etodolac, etoricoxib, fenbufen, fenoprofen, flurbiprofen, ibuprofen, indomethacin, ketoprofen, lumiracoxib, mefenamic acid, meloxicam, nabumetone, naproxen, piroxicam, sulindac, tenoxicam, tiaprofenic acid, ketorolac, metronidazole.

- angiotensin-converting enzyme inhibitors (ACEI) i.e., captopril, cilazapril, enalapril, fosinopril, imidapril, lisinopril, moexipril, perindopril, quinapril, ramipril, trandolapril.

- Angiotensin receptor blockers (ARBs) i.e., azilsartan, candesartan, irbesartan, losartan, Olmesartan, telmisartan, valsartan.

- diuretics i.e., Bendroflumethiazide, chlortalidone, cyclopenthiazide, indapamide, metolazone, xipamide, bumetanide, furosemide, torasemide.

It is worth noting that several other medications can interact with lithium e.g., steroids or reduced lithium levels from e.g., empagliflozin, aminophylline, theophylline. However, these are not included in guidelines as contraindicatory for high-dose lithium and are not included in exclusion criteria.

4) Unable to communicate fluently in English (defined as ability to read and understand the participant information sheet plus ability to communicate with the researcher throughout screening assessment);

5) Suicide risk (assessed using the MINI)

6) Unable to travel to one of the research sites on a regular basis over 6 months;

7) Unable to provide informed consent to participate, for any other reason.

8) Participation in another research study which could potentially influence engagement or outcomes in the present study e.g., presents contraindications with LiOR, examination of another pharmacological or psychological intervention for affective symptoms.

Individuals of any sex/gender can take part. Informed consent to participate will be obtained before inclusion into the study.

## 9.3. Selection of Participants

There will be 4 routes for participant selection:

- 1. Existing database of people interested in research participation, who have consented to be contacted by researchers within the Centre for Affective Disorders team (KCL).
- 2. Community offline and online advertisements: posters in the public domain, online advertising via research portals (e.g., NIHR BRC, MQ), social media posting, advertising campaigns on various platforms, such as Gumtree, to publicise the study to interested potential participants.
- 3. Primary care services i.e. GP mailouts to local patients as coordinated by CRN Portfolio teams (to be confirmed).
- 4. Network of clinicians and services who/which provide care to people with affective disorders within South London & Maudsley NHS Trust.

After potentially eligible individuals are identified through any of these routes, they will be provided with information about the study and a full screening for eligibility will take place subject to verbal consent; for details, see Section 10).

## 9.4. Randomisation Procedure / Code Break

n/a

## 9.5. Blinding Procedures

As an initial feasibility study, there is no blinding included: participants will be made aware of all information regarding the intervention. Researchers undertaking assessments and liaising with participants, as well as the study clinicians and researchers undertaking statistical analyses, will all be aware that this is a single-arm open label study and that no attempts are required to mask whether a participant is currently taking the intervention or whether they have discontinued.

## 9.6. Withdrawal of Participants

We will highlight to all participants that they are free to withdraw from the study at any time, without prejudice or consequences for either their clinical care, or involvement in any other research studies. Similarly, therapy can be discontinued at any point, if a participant withdraws from the study or if a participant decides they no longer wish to continue the intervention. Researchers will also be available throughout the study course to answer further questions about withdrawal. The investigator also has the right to withdraw patients from the therapy and/or study, for any reason e.g., if a participant loses the capacity to consent to the study, they will be withdrawn. This will be assessed by researchers during every contact with participants (e.g., phone calls, study appointments).

Should a participant decide to withdraw from the study, all efforts will be made to report the reason for withdrawal as thoroughly as possible. Importantly, LiOr discontinuation does not constitute as a withdrawal from the study. Thus, should a patient withdraw from the intervention only, efforts will be made to continue to obtain follow-up data, with the permission of the patient; participants who wish to withdraw from LiOR will be asked to confirm whether they are still willing to provide the study data already provided for research.

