## 12.2. Analysis

Intention-to-treat analyses will be undertaken. In a few cases, a sensitivity analysis will be carried out, excluding non-adherent participants (these are specified below, where this applies).

Final analyses will be conducted after data collection has been completed and data cleaned. However, it is worth noting that an interim analysis is planned in May 2025 for all primary analyses below. This is for the purpose of initial pilot data to be included in funding applications being submitted for a feasibility study. No changes to the protocol or any procedures will be made based on this.

Variables will be summarised using descriptive statistics (i.e., mean and standard deviation [SD] or median and interquartile range [IQR] or frequencies and proportions, as appropriate).

Analyses pertaining to each outcome are listed below:

1. LiOR bioavailability as assessed by lithium levels in serum. This will be analysed descriptively, as above. Intraand inter- participant variation will be calculated. Overall changes over time may be assessed using a repeatedmeasures ANOVA (including only adherent participants taking a stable dose) to inform a potential future trial design.

2. LiOR acceptability as assessed by adherence rates (TRQ) and discontinuation. Rates of adherence (< 20% missed) will be assessed descriptively for each timepoint, and extent of adherence will also be described as a continuous (total TRQ score) measure. Rates of discontinuation (participant-report) will be described. Continuous adherence scores (for participants not discontinuing LiOR) over time will be tentatively compared using a repeated-measures ANOVA to inform a potential future trial design.

3. Subjective experiences of LiOR: negative experiences will be described via continuous LiSERS score measure, and positive experiences will be reported as participant-reported rates (yes/no to those listed). LiSERS scores over time (adherent participants only) will be compared using a repeated-measures ANOVA (possibly including dose as a between-subjects factor, pending dose variation within and between participants) to inform a potential future trial design.

4. Protocol feasibility as assessed by the rates (assessed descriptively) of attrition from the study, and of visits missed, and specific data for the putative primary outcomes i.e., mood measures.

There are three secondary outcomes, analysed as exploratory indications of change to inform a future definitive study design:

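### Section 9.6 asks participants who stop only the supplement whether data already given may still be used, which invites selective loss of stoppers' earlier data

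*Protocol*

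**What the plan says.** Protocol section 9.6 separates stopping the supplement from leaving the study: "LiOr discontinuation does not constitute as a withdrawal from the study". It then says that "should a patient withdraw from the intervention only, efforts will be made to continue to obtain follow-up data, with the permission of the patient". After a semicolon, the same sentence adds that those choosing to "withdraw from LiOR will be asked to confirm whether they are still willing to provide the study data already provided for research".

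The synopsis agrees with the first part: "Participants who discontinue will remain in the study, although will not be required to attend intermediary follow- up visits". It adds that they will be asked to come to the final visit.

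For participants who leave the study altogether, section 9.6 provides for recording the reason. It attaches no question about data already collected.

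Section 6.1 makes acceptability co-primary objective 2, measured by self-reported adherence and by discontinuation. Positive and negative experiences are co-primary objective 3. Section 12.2 reports discontinuation as a descriptive rate and states that "Intention-to-treat analyses will be undertaken".

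**The concern.** The question about existing data is triggered by stopping LiOr, and stopping LiOr is itself part of a co-primary outcome. Someone who keeps taking the capsules is not asked. Someone who stops them is asked, although the protocol says that this person is still in the study. Any loss of past data that follows would fall on stoppers only.

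The earlier data of this group are hard to replace. Stoppers need not attend the intermediary visits, so what they gave before stopping, plus a possible week 26 visit, may be all there is. If some refuse, the TRQ, LiSERS, lithium and mood values that describe why and how people came off the supplement are lost, while those of continuers are kept. An analysis plan written later cannot recover data that participants were invited to take back.

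The results are meant to inform the design of a later trial, and section 12.2 also plans an interim look at all primary analyses for funding applications.

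**Working it through.** **1. Who is asked, set side by side**

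| Participant | Status in the protocol | Asked in section 9.6 about data already given? |
|---|---|---|
| Continues LiOr | In the study | No |
| Stops LiOr only | In the study (9.6 and synopsis) | Yes |
| Leaves the study | Withdrawn | No question stated |

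The question is attached to the middle row. It would be expected in the last.

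**2. The plan's own precision figure**

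Inputs from section 12.1: n = 40, a 50% dropout rate, 95% confidence interval of about ±15%.

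Half-width = 1.96 × √(0.5 × 0.5 / 40) = 0.155, or 15.5 points. The Wilson interval is 35.2% to 64.8%, or ±14.8 points. The stated figure reproduces after rounding. It concerns dropout and serves here only as a check.

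**3. What would happen to the discontinuation rate if refusers left the count**

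The protocol does not say that they would. This step is conditional.

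Let x of 40 participants stop and let k of those stoppers be removed.

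- Full rate: x/40
- Rate after removal: (x − k)/(40 − k)
- Difference: (x − k)/(40 − k) − x/40 = −k(40 − x) / [40(40 − k)]

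The difference is negative whenever k > 0 and x < 40, so the direction is fixed. The size depends on x and k. The protocol gives neither a LiOr discontinuation rate nor a refusal rate, so both are assumptions:

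| Stoppers x | Removed k | Full rate | Rate after removal | Shift (points) |
|---|---|---|---|---|
| 8 | 2 | 20.0% | 6/38 = 15.8% | −4.2 |
| 10 | 3 | 25.0% | 7/37 = 18.9% | −6.1 |
| 12 | 3 | 30.0% | 9/37 = 24.3% | −5.7 |
| 20 | 2 | 50.0% | 18/38 = 47.4% | −2.6 |
| 20 | 5 | 50.0% | 15/35 = 42.9% | −7.1 |

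**4. What is exposed even if the count is kept**

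If the fact of stopping is retained for everyone, the discontinuation rate stays at x/40 and step 3 does not apply. The refusers' earlier questionnaire, lithium and mood values would still be at risk. For LiSERS the exposure is mainly in the descriptive summary, because section 12.2 already restricts the comparison over time to adherent participants.

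**The case against.** The strongest reply is that section 9.6 only has people asked. It does not say that data are deleted after a refusal, or that the person or the fact of stopping leaves the count. Section 7.1 separately plans to measure rates and duration of doses taken, and denominator rules may sit in an analysis plan that is not shown. The wording is also awkward enough to be a slip, with the supplement named where the study was meant. All of this stands, and it is why the change in the rate is given only as a conditional illustration. It does not remove the point: the question has little purpose unless a refusal has some effect, and staff will follow the sentence as written.

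A reader might infer more than the documents support:

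- **That refusers' adverse events disappear.** Section 11.3 commits to including documented adverse events reported after consent in the primary study report, with no exception for people who stop LiOr.
- **That the shift could exceed the ±15 points of section 12.1.** With 20 stoppers and 10 removed the rate would be 10/30 = 33.3%, a shift of 16.7 points. That needs half of all participants to stop, half of those to refuse, and the count to be erased as well. The 50% in section 12.1 illustrates precision for dropout and is not an expected LiOr discontinuation rate.
- **That every co-primary result is biased favourably.** The direction is certain only for the discontinuation rate, and only if refusers leave it. Positive experiences would be lost along with negative ones, and removed data recorded as missing would make feasibility look worse.
- **That intention-to-treat is broken.** That principle governs how available data are analysed, and does not settle whether a participant may withdraw permission. The fair statement is that prompting only stoppers fits it poorly.
- **That all who count against acceptability are affected.** Poor adherers who stay on LiOr also count against it, and they are not asked.

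**Conclusion.** The point holds as an internal inconsistency with a real but unquantified risk. Section 9.6 treats LiOr-only stoppers as still in the study and, in the same paragraph, has them alone asked about use of past data. That makes possible loss of earlier data depend on a co-primary outcome. The exposed data are earlier TRQ, LiSERS, lithium and mood values. The discontinuation rate is exposed only if refusers are dropped from it, which the protocol does not state. In that case it can only fall, by about 3 to 7 points in the cases tabulated, all of which rest on assumed stopping and refusal numbers. The sentence should be corrected before it is applied, because the correction is nearly free and the lost data could not be recovered.

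**What to change.** - Limit the question about data already collected to participants who withdraw from the study or withdraw consent, and say what a refusal does.
- For participants who stop LiOr only, ask just for agreement to continued follow-up. Keep data already collected by default, subject to the consent terms, which are not shown here and need checking.
- State that every LiOr discontinuation is counted over all participants enrolled (planned 40).

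The cost is a one-sentence protocol amendment and any matching information-sheet wording. No visits or participants are added, and the right to withdraw consent is unchanged.
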